7. ELIGIBILITY CRITERIA

7.1 INCLUSION CRITERIA

- Subjects who are scheduled for PVC/VT ablation procedure, without structural heart disease
- Age >18 years old and ≤ 80 years
- Fulfil established clinical criteria for catheter ablation of PVC/VT
- Subjects who are at least 18 years or older
- Subjects who have signed an approved Informed Consent Form and applicable subject privacy protection authorization
- Subjects will be selected without regard to gender or age

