8. SUBJECT/PATIENT RECRUITMENT PROCESS

Patient recruitment at a site will only commence once the *study* team has ensured that the following approval/essential documents are in place:

1. HRA approval,
2. Local Site Delegation of Duties and Signature Log is completed (if applicable).

The Royal Brompton Hospital is the single site participating in the trial and will be asked to provide a copy of the following:

1. Signed Clinical *study* Site Agreement (CSSA) (if applicable)
2. Confirmation of capacity and capability

All subjects who wish to enter the study will be fully screened and consented by the Chief Investigator (CI), Principal Investigator or Co-Investigator.

We will recruit patients from those with PVC/VT who have already an indication for catheter ablation according to the current guidelines or have recurrent PVC/VT after previous catheter ablation(s). Patients will be offered participation in the study during the visit in the outpatient clinic. Only one centre will be involved in recruitment of the patients. All electrophysiology consultants in each Trust will be familiar with the protocol and be involved in selection of the patients.

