14.1 SAMPLE SIZE AND RECRUITMENT

This is a feasibility pilot study, which will test the feasibility of PVC/VT foci mapping with Vivo system and catheter ablation in unselected patients without structural heart disease, eligible for PVC/VT ablation. Therefore, no power calculation has been done and the number of patient recruited will be of 15 which are deemed sufficient by the CI and Co-PIs on a clinical basis.

The estimated recruitment period for the trial will be of 6 months. We estimate that this sample size is attainable in practice, as the number of PVC/VT ablation procedures per year performed within the Trust is around 100. We also included patients with previous PVC/VT ablation in order to maximise chances of recruitment. This pilot is performed with the intention to plan a prospective multi-operator/multicentre trial which is adequately powered. We will aim to compare the procedure parameters as well as the outcome of this trial to age & gender matched procedures of the same operators from the last 5 years' database.

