14.3 STATISTICAL ANALYSIS PLAN

Descriptive statistic data with regard to baseline and procedural variables will be reported; continuous variables will be expressed by mean \pm standard deviation or median and interquartile range (25th, 75th percentile), depending on the normality of distribution; categorical variables will be summarized by frequencies and percentages. The outcome of radiofrequency ablation on the entire cohort of patients will be presented in the form of percentage of patients free from symptomatic or documented arrhythmia or with only mild symptoms related to arrhythmia recurrence.

Depending on the severity of symptoms and documentation of tachycardia during follow-up, patients will be divided into two groups (success/recurrence). Baseline characteristics and procedural variables will be compared between these two groups by student t-tests, Mann Whitney U tests, or Fisher's exact test where appropriate in order to identify those variables associated with better mid/long term outcomes. A two-tailed p value <0.05 will be considered statistically significant. Intra-patient improvement from baseline to 6 months follow-up visit will be assessed by McNemar's test. Freedom from PVC/VT will be assessed as a time-dependent variable using Cox proportional hazard models.

To judge if ablation strategy using Vivo mapping system is as successful in achieving the clinical endpoint, we will compare the procedure parameters as well as the outcome of this trial to age & gender matched procedures of the same operator from the last 5 years' database.

To measure the strength of association between the acute successes (PVC/VT suppression at the end of the ablation) and outcome, a McNemar test will be performed. Data will be analyzed using SPSS version 18 (IBM Corporation).

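### The McNemar test of improvement from baseline names no paired variable; if that variable is PVC/VT presence, no patient can worsen and 6 of 15 improved is already significant

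*Combined protocol and SAP*

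**What the plan says.** Section 14.3 plans the test in one sentence: "Intra-patient improvement from baseline to 6 months follow-up visit will be assessed by McNemar"'s test. The same section sets the criterion: "A two-tailed p value <0.05 will be considered statistically significant". It does not name the binary variable that is measured at both times.

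The only outcome dichotomy in 14.3 is built from follow-up data: "Depending on the severity of symptoms and documentation of tachycardia during follow-up, patients will be divided into two groups (success/recurrence"). The favourable outcome, as 14.3 reports it, covers patients free of symptomatic or documented arrhythmia and also those whose recurrence causes only mild symptoms. No baseline counterpart of this classification is given.

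On entry status, Section 7.1 requires that patients "Fulfil established clinical criteria for catheter ablation of PVC/VT", and Section 8 says "We will recruit patients from those with PVC/VT who have already an indication for catheter ablation". On size, Section 14.1 says "the number of patient recruited will be of 15" and "no power calculation has been done".

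The clinical secondary endpoint in Section 14.2.2 is suppression or reduction of PVC burden or VT at 3 months. The charts in Sections 6.3 and 10.5 schedule a Holter recording and a symptom questionnaire before ablation and at 3 months. They contain no 6-month visit.

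**The concern.** McNemar's test uses only patients who change category. Its null hypothesis is that a change for the better and a change for the worse are equally likely. That is a useful hypothesis only if both changes can happen.

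In a study that admits only people who have the arrhythmia, the obvious paired variable, arrhythmia present or absent, leaves no room for worsening. The null hypothesis then amounts to saying that nobody improves. Patients who recur stay in the present-present cell and carry no weight, however many there are.

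At stake is how the 3-month clinical outcome is reported. A majority of recurrences could carry the label of statistically significant intra-patient improvement. Section 14.1 says the pilot is meant to lead to an adequately powered trial, so such a label could mislead the people who plan it.

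**Working it through.** The plan gives no power figure, threshold or expected success rate for this test, so there is no figure to reproduce.

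**Inputs.** n = 15 pairs (Section 14.1). Two-sided significance level 0.05 (Section 14.3). All patients affected at entry (Sections 7.1 and 8). Assumption: all 15 are evaluable at follow-up, since the documents give no dropout rate.

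**Formulas.** Let b be the number improved and c the number worsened.
- Exact: p = min(1, 2 × P(X ≥ max(b, c))), with X ~ Binomial(b + c, 0.5).
- Chi-square on 1 df, continuity-corrected: (|b − c| − 1)² / (b + c).
- Chi-square on 1 df, uncorrected: (b − c)² / (b + c).

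**Case 1: the variable is PVC/VT presence, or success/recurrence with everyone counted as affected at baseline.** Then c = 0 and the exact p value reduces to 2 × 0.5^b.

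| Improved (b) | Not improved | Exact p | Corrected p | Uncorrected p |
|---|---|---|---|---|
| 4 | 11 | 0.125 | 0.134 | 0.0455 |
| 5 | 10 | 0.0625 | 0.074 | 0.025 |
| 6 | 9 | 0.031 | 0.041 | 0.014 |

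For b = 6: 2 × 0.5⁶ = 0.03125; corrected statistic (6 − 1)²/6 = 4.17. For b = 4: uncorrected statistic 4²/4 = 4. The threshold is therefore 6 improved for the exact and corrected forms, and 4 for the uncorrected form. Section 14.3 does not say which form will be used.

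Six of 15 is 40% success, with an exact (Clopper-Pearson) 95% CI of 16% to 68%.

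In this case the exact test is significant whenever at least 6 of 15 succeed. P(Binomial(15, π) ≥ 6) is:

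| True success rate π | 30% | 40% | 50% | 60% | 75% |
|---|---|---|---|---|---|
| Chance of p < 0.05 | 0.28 | 0.60 | 0.85 | 0.97 | >0.99 |

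**Case 2: the variable is a symptom or burden class, so c can exceed zero.**

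| Worsened (c) | Exact p with 6 improved | Smallest b with exact p < 0.05 |
|---|---|---|
| 0 | 0.031 | 6 |
| 1 | 0.125 | 8 (p = 0.039) |
| 2 | 0.289 | 10 (p = 0.039) |

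For c = 1, b = 6: 2 × (7 + 1)/2⁷ = 0.125. For c = 1, b = 8: 2 × (9 + 1)/2⁹ = 0.039, with 7 of 15 patients not improved.

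The result thus depends on a variable the plan leaves open: the same 6 improvers give p = 0.031 with nobody worse and 0.125 with one patient worse.

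**The case against.** A reader might infer that the entry criteria fix the worsening cell at zero whatever is paired. The documents do not support that. Section 14.3 names no variable. Having PVC/VT and an indication for ablation does not place a patient on one side of every possible cut-off. Sections 7.1 and 7.2 set no minimum symptom severity or PVC burden. The favourable outcome in 14.3 admits mild symptoms, so a patient mildly affected at entry could start in it. The endpoint in 14.2.2 includes burden, and a burden threshold can be crossed either way. Section 10.3 also foresees a patient who shows no ventricular arrhythmia at the pre-procedure recording, although that concerns template acquisition and not whether the patient has the condition. This part of the objection stands, and it makes the 6-of-15 result conditional.

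A reader might also infer that a poor result would be hidden, or that the plan offers this p value as evidence for VIVO. Neither follows. Section 14.3 already reports the percentage of patients with a favourable outcome, so 40% would appear beside the p value. It gives the judgement on the VIVO strategy to the matched historical comparison. Nor would the p value nearly always be favourable: at a true success rate of 30% the chance is about 28%.

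Finally, this is a feasibility pilot, Section 14 calls the statistical design purely descriptive, and no decision depends on this test. That limits the harm. It is also a reason to drop the test, because a significance rule does not fit a descriptive design.

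**Conclusion.** The concern holds in conditional form. The plan tests intra-patient improvement without defining the paired variable, and that definition decides whether the test has any content.

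- If the variable is arrhythmia presence, worsening is impossible by design. With 15 evaluable patients, 6 improved and 9 recurring is significant (exact p = 0.031); the uncorrected statistic allows 11 recurring.
- If it is a symptom or burden class, the cell is not empty by design and the threshold rises to 8 improved with one patient worse. The test still starts from a group selected for being affected, so regression to the mean favours improvement, and it discards how much each patient changed.

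Under neither reading does the p value show that the success rate is adequate, or separate VIVO from ablation itself; there is no concurrent control. The figures assume no missing follow-up. Correcting the visit from 6 months to 3 would not remove the problem. The change should be made, but the primary endpoints are not affected.

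**What to change.** In Section 14.3:

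1. Remove the McNemar test of change from baseline.
2. Report success at the 3-month visit, the only follow-up visit in the schedule, as n (%) with an exact 95% CI and no p value. The percentage is already planned; the interval is new. The reference to 6 months goes with the deleted sentence.
3. For intra-patient change, report the median paired change in Holter PVC burden from pre-ablation to 3 months with a 95% CI, for example by the Wilcoxon signed-rank method. State that it is a before-after change not attributable to VIVO.

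Holter burden is preferable to the questionnaire because it matches the endpoint in 14.2.2 and is scheduled at both times, whereas the documents name no questionnaire instrument or score. The plan should define burden and the recording length to be used at both times, and say whether provoked beats count at baseline, since Section 10.3 allows a provocation challenge before the procedure.

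The cost is a few sentences and no additional visits or tests. The downside is the loss of one p value that would probably be favourable at moderate or high success rates.

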10.4 SUBSEQUENT ASSESSMENTS

Follow-up

3 months (follow-up visit – study completion - endpoints assessment)

The next scheduled follow-up visit after discharge will be at approximately three months post PVC/VT ablation. The following assessments will take place:

- Patient's symptoms (questionnaire) and clinical assessment
- Review of medication
- 12-lead ECG
- 12-lead Holter (Mortara)
- If high PVC/ VT burden at 3 months, either therapy change or repeat ablation (according to patient and physician preference).

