10.5 SUMMARY CHART OF STUDY ASSESSMENTS

	Pre-ablation	Pre-discharge	3 months
12 lead ECG		X (routine)	X (routine)
Telemetry	X (routine)		
Contrast CT scan or non-contrast CMR for roadmap	X (routine)		
TTE		x (routine)	
Symptom questionnaire	X (research)		X (research)
Clinic Visit			X (EP OPC)
ECG Holter (Mortara)	X (research)		X (research)

Follow up

3 months
Follow-up visit

RHYTHM & SAFETY
Review therapy, allow Re-ablation if necessary using same methodology
Assess recurrences by 12-lead Mortara Holter

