14. STATISTICAL DESIGN

This is a prospective, non-randomised, observational study which will recruit 15 non-selected patients with PVC/VT eligible for catheter ablation, without structural heart disease.

Procedural outcomes will be compared to age & gender matched procedures of the same operator from the last 5 years' database.

The statistical design was decided in collaboration with the study PIs and will be descriptive only.

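### Section 14.3 tests within-patient improvement only by McNemar's test, on an unnamed variable; a yes/no test discards graded change in either measure charted at both visits, and in 15 patients that can cost power

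*Combined protocol and SAP*

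**What the plan says.** Section 14.3 of the combined protocol and SAP gives one test of change within patients: "Intra-patient improvement from baseline to 6 months follow-up visit will be assessed by McNemar's test". It does not say what is improving or how each visit becomes a yes or a no. McNemar's test appears once more in that section, for acute success against later outcome, which is a different question.

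Section 14.3 also uses symptoms as a graded quantity: "Depending on the severity of symptoms and documentation of tachycardia during follow-up, patients will be divided into two groups (success/recurrence"). Its headline percentage counts patients with only mild symptoms as a good result. Both uses end in two categories.

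Section 10.4 lists "symptoms (questionnaire) and clinical assessment" at the 3-month visit. The chart in 10.5 (also in 6.3) shows "Symptom questionnaire" as a research item before ablation and at 3 months. The Mortara Holter is the only other item charted at both times. No section names the questionnaire or gives its grades or scoring.

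On size and status, section 14.1 says "no power calculation has been done and the number of patient recruited will be of 15". Section 14 says "The statistical design was decided in collaboration with the study PIs and will be descriptive only", yet section 14.3 adds "A two-tailed p value <0.05 will be considered statistically significant".

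**The concern.** McNemar's test needs a yes/no state at each visit and draws its evidence only from patients whose state changes. Suppose the cut were mild or less. A patient going from severe to moderate, or from mild to none, would then count as unchanged. A Holter count reduced to present or absent loses information in the same way: section 4.3.2a has the recorder capture how often each PVC template occurs.

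Two things are at stake. A real improvement in a small cohort may not be detected. And the size of the change is never estimated, because section 14.3 plans no summary of graded within-patient change. The questionnaire is marked as a research item, so patients complete it for the study, and its graded content would go largely unused.

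**Working it through.** The plan states no power or effect size, so it has no figure to reproduce.

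**Inputs from the documents:** 15 patients (14.1); two-sided 5% level (14.3); McNemar's test (14.3); questionnaire and Holter before ablation and at 3 months (10.5).

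**Inputs assumed, because the documents are silent:** the scale, the cut, the baseline mix, the pre-post correlation, the size of the improvement and the version of McNemar's test.

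**Step 1. What exact McNemar needs.** If b patients change one way and none the other, the two-sided exact p is 2 × (1/2)^b.
- b = 5: 2/32 = 0.0625, not significant.
- b = 6: 2/64 = 0.031, significant.

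The smallest significant result is therefore 6 to 0. One change in the opposite direction raises the requirement to 8 to 1: 2 × (1 + 9)/512 = 0.039, whereas 7 to 1 gives 2 × (1 + 8)/256 = 0.070.

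**Step 2. Four-grade model.** Severity is bivariate normal, cut into none/mild/moderate/severe. Baseline mix is 10/30/40/20% or 10/20/40/30%, correlation 0.3 or 0.5, and the McNemar cut is mild or less. Both tests are exact. Power is by simulation, and figures move by a point or two between runs.

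| Improvement (latent SD) | Signed-rank | McNemar | Gain in points |
|---|---|---|---|
| 0.7 | 41–51% | 19–21% | about 20–38 across these three rows |
| 1.0 | 73–83% | 42–47% | |
| 1.3 | 92–97% | 65–74% | |
| 1.6 | – | – | about 11–17 |
| 2.0 | – | – | about 2–9 |

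The gain shrinks at large effects because both tests approach 100%.

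**Step 3. Continuous model.** Severity is not grouped for the signed-rank test. The effect is the mean change divided by the SD of the change, dz = shift/√(2(1 − correlation)). Correlation is 0.5 and the cut lies midway between the visit means.

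| dz | Signed-rank | Exact McNemar | Loss | Loss with uncorrected chi-square McNemar |
|---|---|---|---|---|
| 0.5 | 41% | 9% | 32 | 18 |
| 0.8 | 80% | 29% | 51 | 30 |
| 1.0 | 94% | 48% | 46 | 26 |
| 1.5 | about 100% | 87% | 13 | 5 |
| 2.0 | about 100% | 99% | 1 | 0 |

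The version of the test matters: uncorrected chi-square is (4 − 0)²/4 = 4 at 4 to 0, above the 5% critical value of 3.84, so it needs fewer changes than the exact test. The plan does not say which is meant.

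**Step 4. Where the loss vanishes or grows.** In a four-grade model with everyone moderate or severe at baseline, the loss is 18 points if 20% become symptom-free, 6 at 40%, and 0–1 at 50% or more. With half the patients already at none or mild, it reaches 61 points. If all 15 start in the bad state, exact McNemar power is P(X ≥ 6) for X binomial(15, p): 60%, 85% and 97% for p = 0.4, 0.5 and 0.6.

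In every scenario examined, the graded test had power equal to or above McNemar's. The gap ran from about 0 to over 60 points.

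**The case against.** The strongest reply is that the plan never ties McNemar's test to the questionnaire. A reader might infer that it does, because the sentence closely follows the grouping by symptom severity. The text does not say so. The listed clinical secondary endpoint (14.2.2) is PVC burden or VT, so improvement could mean arrhythmia. This stands, and it rules out saying that the plan dichotomises the questionnaire. It does not remove the point: either measure charted at both visits can carry graded information, and if symptoms were never meant, the questionnaire has no within-patient analysis at all.

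The scale and cut are also not in the plan. The mild-symptom wording belongs to a composite outcome after ablation and is not given as the McNemar threshold. If the form is only a checklist, there may be no score to rank until a scoring rule is written. This stands too.

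A reader might also take a loss of 20 to 35 points as a property of a 15-patient study. It is not. The figure depends on the assumed effect, mix, cut and test version, and it falls close to zero when the treatment effect is very large.

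Finally, symptoms are not a listed endpoint, the primary efficacy endpoint is procedure time, and the study is a pilot described as descriptive. That limits the weight. It does not favour McNemar's test: a change with an interval describes more than a p-value from a yes/no table. Nor do the documents say that the later multicentre trial in 14.1 will use symptoms as an endpoint, so no claim is made that it depends on this result.

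**Conclusion.** The point holds in a limited form. Section 14.3's only test of within-patient improvement is a yes/no test on an unnamed variable with an unstated cut, while both candidate measures can be analysed on a finer scale. The direction of the loss is secure. Its size is not: about 20–38 points under the four-grade assumptions at 0.7–1.3 SD, about 11–17 at 1.6 SD, about 2–9 at 2.0 SD, and about 0 to over 60 across the other models tried. The lack of any planned estimate of graded change matters at least as much as the power. This is a worthwhile, inexpensive improvement to an exploratory analysis; it does not undermine the study's main conclusions.

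**What to change.** In 14.3, name the questionnaire and its scoring. State that symptom change from pre-ablation to 3 months is analysed within patients on the full score or grade, by exact Wilcoxon signed-rank test, with the Hodges-Lehmann median change and its 95% confidence interval. Keep the percentage with no or only mild symptoms as a supplementary summary. If McNemar's test is kept beside it, state its variable, cut and version. The 6-month visit in the McNemar sentence must also be reconciled with the 3-month follow-up in 6.1 and 10.4.

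The cost is a sentence or two of SAP text plus a scoring rule. No new patients, visits or data are needed. The one drawback is that the main result becomes a change in score, which is less immediate than a percentage; the retained summary covers that.

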6.2 TREATMENT AND RATIONALE

[figure not shown]
A three month follow up period after ablation of PVC/VT is a long enough time frame which allows us to assess the effect of the ablation on suppression/reduction of arrhythmia burden. Patients will be followed-up at 3 months following the ablation procedure. Early recurrences will be treated by uptitrating/changing/addition of anti-arrhythmic medication and/or DCCV if persistent arrhythmia. If further arrhythmia occurs despite these measures, a re-ablation procedure will be offered. If further episodes occur, patients can be offered a second ablation procedure or continuation of medical management.

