14.2.2 Secondary endpoints

- To assess clinical outcome (suppression of reduction of PVCs burden/VT at 3 months F/U)
- To assess safety
- To assess economical outcome (cost reduction per case)

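### The outcome rules in 14.3 do not measure the PVC-burden endpoint of 14.2.2: as written, the Cox outcome fails almost every PVC patient, while the success/recurrence grouping can pass one whose burden has not changed

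*Combined protocol and SAP*

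**What the plan says.** Section 14.2.2 gives the secondary clinical endpoint as "To assess clinical outcome (suppression of reduction of PVCs burden/VT at 3 months F/U". Two other sections fit with it. Section 6.2 justifies the three-month follow-up because it "allows us to assess the effect of the ablation on suppression/reduction of arrhythmia burden", and 10.4 acts on the burden only when it is high: "If high PVC/ VT burden at 3 months, either therapy change or repeat ablation". Neither the size of a reduction nor the meaning of high is quantified.

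Section 14.3 then uses three outcome rules:

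- **Percentage:** "percentage of patients free from symptomatic or documented arrhythmia or with only mild symptoms related to arrhythmia recurrence".
- **Grouping:** "Depending on the severity of symptoms and documentation of tachycardia during follow-up, patients will be divided into two groups (success/recurrence".
- **Cox model:** "Freedom from PVC/VT will be assessed as a time-dependent variable using Cox proportional hazard models".

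The follow-up box in 10.5 says how recurrence is found: "Assess recurrences by 12-lead Mortara Holter". The recording length is not stated. Mortara recordings are scheduled before ablation and at 3 months (6.3, 10.5).

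**The concern.** The endpoint is a change in a quantity, PVC burden. The rules in 14.3 work from the presence of arrhythmia, from symptoms, or from tachycardia, and none refers to burden. A rule that any PVC breaks and a rule that no number of isolated PVCs breaks will both miss the difference between a patient whose burden has nearly gone and one whose burden is unchanged.

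The same patient can then be a success in one analysis and a failure in another, and the choice between them is left open until the data are in. The study is also meant to inform a larger powered trial (14.1), so an outcome that cannot separate responders from non-responders would be carried forward.

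**Working it through.** The plan states no figure to reproduce: the 15 patients were chosen on clinical grounds without a power calculation (14.1). The check has two parts.

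**1. Classify two illustrative patients under each rule.** Both were ablated for PVCs, have no symptoms at 3 months and have no documented tachycardia. Patient A goes from 20% burden to 0.2% (a 99% fall). Patient B stays at 20%. The burdens are illustrations, not figures from the documents.

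| Rule | A (99% fall) | B (no change) |
|---|---|---|
| 14.2.2, burden reduced | benefit | no benefit |
| 14.3 percentage | success, if the mild-symptom limb includes no symptoms | success, on the same reading |
| 14.3 grouping | success | success |
| 14.3 Cox, as written | event | event |

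Only 14.2.2 separates A from B. The Cox rule calls both failures and the grouping calls both successes. An isolated PVC is not tachycardia, so B gives the grouping nothing to count.

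**2. How often would a good responder be a Cox event?** The documents give no heart rate, recording length or baseline burden. Assume 70 beats/min and Poisson counts.

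- Expected PVCs = 70 × 60 × hours × baseline burden × (1 − reduction)
- P(at least one) = 1 − exp(−expected)

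In 24 hours there are 70 × 60 × 24 = 100,800 beats, so a 20% baseline is 20,160 PVCs and a 10% baseline is 10,080.

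| Recording | Baseline | Reduction | Expected PVCs | P(at least one) |
|---|---|---|---|---|
| 24 h | 20% | 99% | 201.6 | about 1 |
| 24 h | 20% | 99.9% | 20.2 | about 1 |
| 24 h | 20% | 99.99% | 2.0 | 0.87 |
| 24 h | 10% | 99.99% | 1.0 | 0.64 |
| 1 h | 20% | 99% | 8.4 | 0.9998 |
| 1 h | 10% | 99% | 4.2 | 0.985 |

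Starting from a count instead, a low baseline of 500 PVCs per 24 hours leaves 5 after a 99% fall, and P = 1 − exp(−5) = 0.993. Among 15 such patients, the expected number with no PVC on the recording is 15 × 0.0067 = 0.1. Clustering of PVCs would lower these probabilities, mainly where the expected count is only a few.

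One patient in 15 is 100/15 = 6.7 percentage points.

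**The case against.** A fair defence makes five points.

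- **The plan never says that one Holter PVC is an event.** The Cox event is undefined, and 6.2 and 10.4 point away from so strict a rule. This is right as to intent: the documents do not show that the sponsor means to score a single PVC as failure. But the only words given are freedom from PVC/VT, with no threshold and no event date, so the text as it stands supports nothing milder.
- **The percentage outcome is not at fault in the same way.** A reader might infer that patient A also fails there, or that a symptom-free patient with a few PVCs ranks below a mildly symptomatic one. The documents do not support that. The second limb accepts recurrence with only mild symptoms. That is naturally a ceiling, and having no symptoms falls under it.
- **A reader might infer that 14.3 misplaces the best responders throughout.** It does not: the grouping counts A as a success. Its weakness is that it counts B as one too.
- **The numbers rest on assumptions.** They do. They show that residual PVCs will be seen, not how the sponsor would score them. The result is stable over the baselines and recording lengths tried.
- **The baseline recording may not support a ratio.** Section 10.3 describes a ward recording made to capture arrhythmia templates, with exercise, isoprenaline or atropine available if none appears. It may be short, provoked or free of PVCs. This stands, and the fix has to allow for it.

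The endpoint is also secondary, in an unpowered pilot that section 14 calls descriptive.

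**Conclusion.** The concern holds for two of the three rules. As written, the Cox outcome is far stricter than 14.2.2: under the stated assumptions a patient with a 99% fall in burden is an event with probability 0.985 or more. The grouping is too lax for PVC patients, because a symptom-free patient with no change in burden is a success. The percentage is led by symptoms rather than burden, but it is not clearly wrong.

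The mismatch between 14.2.2 and 14.3 follows from the text alone. The size of the Cox problem rests on the assumed heart rate, recording length, baseline burden and Poisson counts. For a secondary outcome in a 15-patient descriptive study this should be corrected before analysis, but it does not threaten the primary endpoints.

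**What to change.** In 14.3, for patients ablated for PVCs:

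1. Analyse PVC burden from the scheduled pre-ablation and 3-month Mortara recordings as the within-patient change. Express it as a rate or a percentage of beats, so that recordings of different length can be compared.
2. Define recurrence once: 3-month burden above a pre-specified fraction of the patient's own baseline, or any documented VT. The sponsor should choose the fraction before data are seen, since the documents offer no figure for it.
3. Use that definition in the success/recurrence grouping, and in any freedom-from-arrhythmia analysis in place of freedom from PVC/VT.
4. Take the baseline only from the unprovoked part of the recording, and report patients without a usable unprovoked baseline separately.
5. Keep symptom status and complete absence of PVCs as separate descriptive lines.

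No new visit or test is needed. The costs are that the sponsor must commit to a threshold in advance, the unprovoked part of the baseline recording must be identifiable, and a few of the 15 patients may drop out of the burden analysis. The change serves the VIVO cohort only: the retrospective cohort has no follow-up (6.1), so it does not supply a 3-month burden for the historical comparison.
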